| Excluded based on Inclusion # 3b - Acute Symptomatic PE and based on Inclusion # 4 - Age                                                                                                                                                                                                                                                      | -4,641   | 8,593   | -2852    | 8,382   | -21,229    | 20,793    |
| Excluded based on Exclusion # 1 - pregnancy                                                                                                                                                                                                                                                                                                   | -14      | 8,579   | -42      | 8,340   | -22        | 20,771    |
| Excluded based on Exclusion # 6 - Thrombectomy, Insertion of Caval Filter, or Use of Fibrinolytic Agent                                                                                                                                                                                                                                       | -211     | 8,368   | -143     | 8,197   | -24        | 20,747    |
| Excluded based on Exclusion # 7 - Active bleeding (HAS_BLED Score >=3), based on Exclusion # 10A - Mechanical Valve, and based on Exclusion # 11.1 - Intracranial Bleeding                                                                                                                                                                    | -3,708   | 4,660   | -1447    | 6,750   | -11,558    | 9,189     |
| Excluded based on Exclusion # 11.2 - Intraocular Bleeding                                                                                                                                                                                                                                                                                     | 0        | 4,660   | 0        | 6,750   | 0          | 9,189     |
| Excluded based on Exclusion # 11.3 - Gastrointestinal Bleeding                                                                                                                                                                                                                                                                                | -12      | 4,648   | -52      | 6,698   | -78        | 9,111     |

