| Excluded based on Exclusion # 11.4 - Head Trauma or Other Major Trauma                                                                                                                                                                                                                                                                        | -60      | 4,588   | -65      | 6,633   | -96        | 9,015     |
| Excluded based on Exclusion # 11.5 - Major Surgery, Exclusion # 11.6 - Ischemic Stroke, Exclusion # 11.7 – Neurosurgery, Exclusion # 11.8 - Gross Hematuria, Exclusion # 11.9 - Non - healing surgical wound, Exclusion # 11.10 - Intracranial neoplasm, arteriovenous malformation or aneurysm, and Exclusion # 11.11 - Overt Major Bleeding | -57      | 4,531   | -33      | 6,600   | -111       | 8,904     |
| Excluded based on Exclusion # 11.12 - Coagulation defects or malignant neoplasm of tissue                                                                                                                                                                                                                                                     | -36      | 4,495   | -20      | 6,580   | -33        | 8,871     |
| Excluded based on Exclusion # 12 - active liver disease                                                                                                                                                                                                                                                                                       | -133     | 4,362   | -142     | 6,438   | -226       | 8,645     |
| Excluded based on Exclusion # 13 - CCI >= 10 and based on Exclusion # 14 - Bacterial Endocarditis                                                                                                                                                                                                                                             | -39      | 4,323   | -33      | 6,405   | -28        | 8,617     |

|                                                                                                                             |     |              |     |              |      |              |
|-----------------------------------------------------------------------------------------------------------------------------|-----|--------------|-----|--------------|------|--------------|

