| Subjects with a provoked index event without the existence of a persistent risk factor for recurrence as described in the eligibility checklist                                                                                                                                                                                                                                                                                                                                                      | N/A                                                                                                                                                                                                                                                         |                                                                                                                                                                                                                                                                                  |                                                                                                                                                                                                                                                                                                                                                                                                                                                                                                                    |

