# Appendix A

|                                                                                                                                                                                                     |                                                                                                                                                                                                                                                                                                                                                                                                                       |                                                                                                                                                                                       |  |
|-----------------------------------------------------------------------------------------------------------------------------------------------------------------------------------------------------|-----------------------------------------------------------------------------------------------------------------------------------------------------------------------------------------------------------------------------------------------------------------------------------------------------------------------------------------------------------------------------------------------------------------------|---------------------------------------------------------------------------------------------------------------------------------------------------------------------------------------|--|
| 
Thrombectomy, insertion of a caval filter, or use of a fibrinolytic agent to treat the current episode of venous thromboembolism (VTE).
                                                      | 
Measured 30 days prior and including the day of drug initiation in any diagnosis position in an inpatient or ED care setting
 
Thrombectomy:
CPT codes: 37184, 37185, 37186, 37187, 37188
HCPCS codes: C1757
 
Caval filter:
CPT codes: 37191, 37192, 37193
HCPCS codes: C1880
 
Fibrinolytic agent:
streptokinase, alteplase, reteplase, tenecteplase
 | 
Components will act as both exclusion criterion and censoring events
                                                                                                           |  |

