| Head trauma or other major trauma                           | 
Measured 60 days prior to and including the day of drug initiation in any diagnosis position and in an inpatient or outpatient care setting
 
See 'Major Trauma' sheet for codes
                                                                                                                                                                                                                                                                                                                                                                                                                                                                                                                                                                                                                               |  |  |
| Major surgery                                               | 
Measured 60 days prior to and including the day of drug initiation in any diagnosis position and in an inpatient or outpatient care setting
 
Major surgery selected from codes range 35.x- 84.x
                                                                                                                                                                                                                                                                                                                                                                                                                                                                                                                                                                                                               |  |  |

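### The 60-day major-surgery exclusion (#11.5) may under-capture surgery, its effect cannot be verified from the document, and no recent major-surgery covariate backs it up

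*Combined protocol and SAP*

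**What the plan says.** Section 5.3 applies the exclusions in sequence. Major surgery has no row of its own. It is reported with ischemic stroke, neurosurgery, gross hematuria, non-healing surgical wound, intracranial lesions and overt major bleeding, in a row that begins "Excluded based on Exclusion # 11.5 - Major Surgery, Exclusion # 11.6 - Ischemic Stroke". The removed and remaining counts for Optum, MarketScan and Medicare are "57 | 4,531 | -33 | 6,600 | -111 | 8,904".

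Appendix A gives the criterion as "Measured 60 days prior to and including the day of drug initiation in any diagnosis position and in an inpatient or outpatient care setting", followed by "Major surgery selected from codes range 35.x- 84.x". It names no coding system and does not list the selected codes. The mechanical-valve row of the same appendix labels codes beginning 35 as ICD-9 procedure codes, so the range reads as ICD-9. The opening rows of Appendix A say that ICD-10 codes are left out for space, that full lists are in an external folder, and that ICD-9 codes were converted with a mapping macro.

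Two other rows of Appendix A bear on this. The trial criterion "Subjects with a provoked index event without the existence of a persistent risk factor for recurrence" is marked N/A. The qualifying DVT or PE may be recorded at any time in the 180 days up to and including drug initiation.

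**The concern.** AMPLIFY excluded recent major surgery because of bleeding risk. Surgery is also a transient cause of VTE, which generally means a lower risk of recurrence afterwards. It therefore bears on both the primary outcome and the major bleeding outcome. If surgical patients stay in the cohort, and if recent surgery also influences the choice between apixaban and warfarin, both hazard ratios are open to confounding by something the propensity score does not measure directly.

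Three features prompt the question. The count is small for seven criteria combined. The printed definition has no outpatient procedure coding, whereas for thrombectomy the plan prints "CPT codes: 37184, 37185, 37186, 37187, 37188". ICD-10 procedure codes are printed for valves and neurosurgery but not for major surgery, so the general note on space does not account for the difference between rows.

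**Working it through.** **1. Reproduce the flowchart row.** The starting counts are those left after the trauma row, "60 | 4,588 | -65 | 6,633 | -96 | 9,015".

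| | Optum | MarketScan | Medicare | Total |
|---|---|---|---|---|
| Before row #11.5–11.11 | 4,588 | 6,633 | 9,015 | 20,236 |
| Removed | 57 | 33 | 111 | 201 |
| After row | 4,531 | 6,600 | 8,904 | 20,035 |
| Share removed | 1.24% | 0.50% | 1.23% | 0.99% |

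The subtractions are exact, and 201/20,236 = 0.99%. Since seven criteria share the row, this is an upper bound for surgery alone among patients still present at that step.

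**2. What had already been removed.** The row containing HAS-BLED, mechanical valve and intracranial bleeding comes earlier: "3,708 | 4,660 | -1447 | 6,750 | -11,558 | 9,189". Its starting counts are 8,368 + 8,197 + 20,747 = 37,312, and it removes 3,708 + 1,447 + 11,558 = 16,713 (44.8%). Trauma, with the same 60-day window and settings as surgery, then removes 60 + 65 + 96 = 221 of 4,648 + 6,698 + 9,111 = 20,457 (1.08%). Surgical patients caught by any earlier row are counted there.

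**3. Is 201 too few?** The documents give no share of patients with major surgery in the prior 60 days. The shares below are assumptions, applied to 20,236.

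| Assumed share | A complete exclusion removes | Shortfall against 201 |
|---|---|---|
| 1% | 202 | about 1 |
| 2% | 405 | at least 204 |
| 5% | 1,012 | at least 811 |
| 10% | 2,024 | at least 1,823 |

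The count is too low only if the true residual share is clearly above 1%.

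**4. If only ICD-9 procedure codes had been run.** This is conditional, and it assumes a US changeover to ICD-10 on 1 October 2015, a date not in the documents. The share of entry days in section 5.2.1 after that date would be 823/1,229 = 67% (Medicare), 1,188/1,594 = 75% (MarketScan) and 1,644/2,050 = 80% (Optum). These are calendar days, not patients, and nothing shows that the condition holds.

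**5. A check against the cohort's own data.** In the unmatched Table 1 for MarketScan, 2,325 + 3,266 = 5,591 of 6,338 patients (88.2%) had a hospital stay in the prior 30 days, and 279 + 830 = 1,109 (17.5%) had one on days 31–180. Yet this database has the lowest removal share, 0.50%. Many of the recent stays will be for the index VTE, so this is a reason to check and no more.

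**6. What Table 1 covers.** It lists peripheral vascular disease or its surgery, coronary procedures, cerebrovascular procedures, fractures, immobilization (unmatched table), major trauma with likely prolonged hospitalization (matched table), and hospitalization and hospital-day counts. There is no row for recent general or orthopedic major surgery.

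**7. The windows side by side.** Qualifying VTE: 180 days. Major-surgery exclusion: 60 days. Provoked-VTE criterion: N/A. Surgery on days 61–180 is outside the exclusion and reaches the propensity score only through the proxies in step 6.

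**The case against.** A reader might infer from the 1.0% and the ICD-9 range that the exclusion does not work. The documents do not support that. They give no benchmark for surgery; at a residual share of 1%, about 202 removals would be expected. The row is what remains after large earlier exclusions. The comparison with trauma says little, because a patient with both is counted under trauma. The wording implies a selected subset of codes held elsewhere, and Appendix A refers readers to the external folder for missing information. Other rows print only ICD-9 codes too. One is liver disease (apart from hepatorenal syndrome), whose row still removes 133 + 142 + 226 = 501 of 4,495 + 6,580 + 8,871 = 19,946 patients (2.5%). A printed ICD-9 list is therefore weak evidence that only ICD-9 was run.

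A reader might also infer that nothing else deals with surgery. That goes too far. Several related proxies are balanced in the pooled matched cohort (warfarin against apixaban): fractures 5.3% and 5.9%, hospitalization within 30 days 80.3% and 81.1%, hospitalization on days 31–180 23.8% and 23.3%, and mean hospital days 5.63 and 5.47. Nor do the documents show that recent surgery differs between the drugs. It is also fair that the trial criterion is two months, so balancing days 61–180 goes beyond copying that criterion.

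These arguments defeat a claim of failure. They do not supply the count for #11.5, the codes used, or a direct measure of recent surgery. The external folder may contain CPT codes, but the stated reason for omission concerns ICD-10 lists only.

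**Conclusion.** The point holds in a limited form. The effect of #11.5 cannot be verified from the document, and the criterion may under-capture surgery. What is established is that it and six other criteria together remove at most 1.0% of patients (0.50% in MarketScan), that the printed definition is one range reading as ICD-9 procedure codes with no CPT codes despite an outpatient search, and that Table 1 has no recent general or orthopedic major-surgery covariate. The gap on days 61–180 follows from the stated windows and does not depend on which code lists were run.

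The number of surgical patients left in is unknown. The 204 to 1,823 shortfall rests on an assumed share of 2% to 10%, and the 67%, 75% and 80% figures on an assumed ICD-9-only run. Neither is a finding about this cohort. Bias in the hazard ratios further requires that surgery is related to drug choice after matching on the existing proxies, which the documents neither show nor exclude.

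**What to change.** Before the comparative analyses, for which the report and date fields in section 13 are still blank:

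1. Confirm that #11.5 runs on CPT and ICD-10 procedure codes as well as ICD-9. Re-run it if it does not, and state the coding systems and the selected list in Appendix A.
2. Give #11.5 its own flowchart row for each database.
3. Add major surgery in the 180-day baseline to Table 1 and to the propensity score. This covers days 61–180; it cannot reach surgery that preceded a VTE recorded near the start of that window.

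The cost is one code list, one flowchart row, one covariate and a re-run, with possibly slightly fewer matched patients. The stated pooled power reproduces as Φ(√(98.1036 × 0.25) × (ln 1.8 − ln 0.84) − 1.96) = 0.965. If expected events fell by 5% or 10% (illustrative), to 93.2 or 88.3, the same formula gives 0.957 or 0.947.

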## 6. Variables

### 6.1 Exposure-related variables:

#### Study drug:

The study exposure of interest is initiation of apixaban. New initiation will be defined by no use of apixaban or warfarin in the prior 6 months before treatment initiation (washout period).

#### Comparator:

New initiators of warfarin, defined by no use of apixaban or warfarin in the prior 6 months.

### 6.2 Covariates:

- Age
- Sex
- Combined Comorbidity Index (CCI), measured over the baseline covariate assessment period, defined as 180 days prior to and including index date

Covariates listed above represent only a small subset of covariates that will ultimately be controlled for in the design and analysis. We use the covariates above only for initial feasibility analyses to judge whether there is likely to be sufficient overlap between treatment groups to proceed with the study. Remaining covariates are defined only after the study has passed the initial feasibility analysis and the initial power assessment and are listed in Table 1 (**Appendix B**).

### 6.3 Outcome variables and study follow-up:

#### 6.3.1 Outcome variables

Primary Effectiveness outcomes of interest: (definitions provided in **Appendix A**):

- **Primary Outcome:** VTE and cause-specific mortality
- **Secondary Outcome:** Individual components
  - Hospital admission for VTE (principal diagnosis position)
  - Cause-specific mortality
    - Inpatient mortality identified using discharge status codes from hospitalization for VTE

Safety outcome of interest:

1. Major bleeding

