#### 6.3.2 Study follow-up

Both as-treated (AT) and intention-to-treat (ITT) analyses will be conducted with treatment defined as the index drug on the day of cohort entry. Because adherence in the real-world databases is expected to be much worse than in the trial, the AT analysis is the **primary** analysis, as it targets the relative hazard of outcomes on treatment.

For the AT analyses, the follow-up will start the day after initiation of apixaban and comparator and will continue until the earliest date of the following events:

- The first occurrence of the outcome of interest, unless otherwise specified for selected outcomes,
- The date of end of continuous registration in the database,
- End of the study period,
- Measured death event occurs,
- Nursing home admission

- Nursing home admissions are considered a censoring event because the data sources utilized typically provide little to no data on a patient, particularly on drug utilization, after admission. We will utilize this as an exclusion reason for cohorts for the same reason.
- The date of drug discontinuation, defined as the date of the last continuous treatment episode of the index drug (apixaban and comparator) plus a defined grace period (i.e., 10 days after the end of the last prescription's days' supply in main analyses).
- The date of augmentation or switching from exposure to comparator or vice versa or augmentation/switching to any other NOAC (e.g. switching from apixaban to rivaroxaban would be a censoring event);
  - A dosage change on the index treatment does not fulfill this criterion
  - An added treatment that is not part of the exposure or comparator group does not fulfill this criterion
- Treatment of current episode of VTE with thrombectomy, insertion of caval filter, or use of fibrinolytic agent (streptokinase, alteplase, reteplase, tenecteplase)

For the intention-to-treat (ITT) analyses, the censoring based on the augmentation/switching and treatment discontinuation will be replaced with a maximum allowed follow-up time of 365 days.

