# Appendix A

| AMPLIFY trial definitions                                                                                                                                                                                                                                                                                                                                                                                                                                                                            | Implementation in routine care                                                                                                                                                                                                                              | Please see the following Google Drive for further details or any missing information:
https://drive.google.com/drive/folders/1WD618wrvwYIeaXzflTcuK-VCcnb6b-gV?usp=sharing |                                                                                                                                                                                                                                                                                                                                                                                                                                                                                                                    |

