# Appendix A

|                                            |                                                                                       |
|--------------------------------------------|---------------------------------------------------------------------------------------|
| Title                               |                                                                                       |
| Venous Thromboembolism (VTE)               |                                                                                       |
| ICD-9 Dx inpatient primary position |                                                                                       |
| PE                                  |                                                                                       |
| 415.1                                      | PULMONARY EMBOLISM AND INFARCTION                                                     |
| 415.11                                     | IATROGENIC PULMONARY EMBOLISM AND INFARCTION                                          |
| 415.19                                     | OTHER PULMONARY EMBOLISM AND INFARCTION                                               |
| DVT                                 |                                                                                       |
| 451.1                                      | PHLEBITIS AND THROMBOPHLEBITIS OF DEEP VEINS OF LOWER EXTREMITIES                     |
| 451.11                                     | PHLEBITIS AND THROMBOPHLEBITIS OF FEMORAL VEIN (DEEP) (SUPERFICIAL)                   |
| 451.19                                     | PHLEBITIS AND THROMBOPHLEBITIS OF OTHER                                               |
| 451.2                                      | PHLEBITIS AND THROMBOPHLEBITIS OF LOWER EXTREMITIES UNSPECIFIED                       |
| 451.81                                     | PHLEBITIS AND THROMBOPHLEBITIS OF ILIAC VEIN                                          |
| 451.9                                      | PHLEBITIS AND THROMBOPHLEBITIS OF UNSPECIFIED SITE                                    |
| 453                                        | BUDD-CHIARI SYNDROME                                                                  |
| 453.1                                      | THROMBOPHLEBITIS MIGRANS                                                              |

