# Appendix A

|                                             |                                                                                            |
|---------------------------------------------|--------------------------------------------------------------------------------------------|
| 453.9                                       | EMBOLISM AND THROMBOSIS OF UNSPECIFIED SITE                                                |
| ICD-10 Dx inpatient primary position |                                                                                            |
| PE                                   |                                                                                            |
| I26.0                                       | Pulmonary embolism with acute cor pulmonale                                                |
| I26.01                                      | Septic pulmonary embolism with acute cor pulmonale                                         |
| I26.02                                      | Saddle embolus of pulmonary artery with acute cor pulmonale                                |
| I26.09                                      | Other pulmonary embolism with acute cor pulmonale                                          |
| I26.9                                       | Pulmonary embolism without acute cor pulmonale                                             |
| I26.99                                      | Other pulmonary embolism without acute cor pulmonale                                       |
| DVT                                  |                                                                                            |
| I80.1                                       | Phlebitis and thrombophlebitis of femoral vein                                             |
| I80.10                                      | Phlebitis and thrombophlebitis of unspecified femoral vein                                 |
| I80.11                                      | Phlebitis and thrombophlebitis of right femoral vein                                       |
| I80.12                                      | Phlebitis and thrombophlebitis of left femoral vein                                        |
| I80.13                                      | Phlebitis and thrombophlebitis of femoral vein, bilateral                                  |

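### Does the death component of the primary composite add anything, and must the outcome be renamed because it does not?

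*Combined protocol and SAP*

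**What the plan says.** Section 6.3.1 makes the primary outcome a composite of VTE and cause-specific death, and lists its two components separately as secondary outcomes. The first is "Hospital admission for VTE (principal diagnosis position"). The second is "Inpatient mortality identified using discharge status codes from hospitalization for VTE". No diagnosis position is given for the second.

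Section 6.3.1 refers to Appendix A for definitions. There the primary-outcome row gives only a timing and a citation to a validation study. The VTE code lists are headed "ICD-9 Dx inpatient primary position" and "ICD-10 Dx inpatient primary position". No separate definition of VTE death is visible, but the header row of Appendix A points to an external folder for "further details or any missing information".

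Under Section 6.3.2, as-treated follow-up starts the day after initiation and ends at the earliest of several events. These include "The first occurrence of the outcome of interest, unless otherwise specified for selected outcomes" and "Measured death event occurs". For the intention-to-treat analysis only the switching and discontinuation rules change: they "will be replaced with a maximum allowed follow-up time of 365 days". Censoring at death remains.

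The endpoint being emulated (Section 1.3) is recurrent symptomatic VTE or VTE-related death, with no restriction to hospital.

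**The concern.** A composite that names death suggests that death can contribute events of its own. Here the death component appears to lie inside the admission component, so in a time-to-first-event analysis it would be redundant. VTE deaths outside a VTE admission would not be outcomes at all.

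The study exists to be compared with a trial whose endpoint counts VTE-related death. A reader who saw only the label might think the two endpoints match more closely than they do. The document also leaves open two details that could change the count: the diagnosis position for the death component, and whether a stay already open at the start of follow-up can contribute a death. The obvious responses are to rename the outcome, to spell out the definition, and to add a sensitivity analysis that counts any recorded death.

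**Working it through.** **Which first events can the death component add?** Taking Sections 6.3.1 and 6.3.2 together:

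1. A principal-position VTE admission during follow-up, discharged alive, is counted at admission.
2. The same admission ending in death is also counted at admission. The death comes no earlier than the admission, so it adds no first event.
3. A VTE stay that began on or before the index day and ends in death during follow-up could be counted only as a death. The number of such stays is not given.
4. A death in a stay with VTE in a secondary position counts only if an unseen rule in the external folder allows it.
5. A VTE death outside any VTE stay is not an outcome. If recorded, it censors follow-up. If unrecorded, follow-up ends under another rule, such as end of enrollment or discontinuation.

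On the natural reading only case 3 can add anything. Case 4 depends on a rule that is not visible.

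**The plan's power (Section 10).** Inputs: 7,140 matched patients, risk 13.74 per 1,000, HR 0.84, margin 1.8, two-sided alpha 0.05.

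- Events = 7,140 × 13.74 / 1,000 = 98.10.
- Power = Φ(√(events/4) × [ln 1.8 − ln 0.84] − 1.96) = Φ(4.952 × 0.762 − 1.96) = Φ(1.814) = 0.965, as stated.

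**Effect of treating the outcome as VTE hospitalization only.** On the natural reading no event is lost, so both figures stand. The share of events that arise only as deaths (cases 3 and 4) is not given, so I assume a range and remove them:

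| Assumed share | Events left | Power |
|---|---|---|
| 0% | 98.1 | 0.965 |
| 1% | 97.1 | 0.964 |
| 2% | 96.1 | 0.962 |
| 5% | 93.2 | 0.957 |
| 10% | 88.3 | 0.947 |

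**What an any-death sensitivity analysis would contain.** The censoring table in Section 9 shows 103 deaths in 7,140 patients (49 warfarin, 54 apixaban). These are recorded deaths from any cause, in a dummy-outcome run with as-treated censoring. They do not bound unrecorded deaths or deaths in the longer intention-to-treat follow-up.

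- If none overlaps with a VTE event, total events = 98.1 + 103 = 201.1, and the non-VTE share = 103 / 201.1 = 51.2%. This is a worst case, because the dummy run does not stop at VTE and some of these deaths may follow a VTE admission.
- At a VTE HR of 0.84 the 98.1 events split into 44.8 apixaban and 53.3 warfarin. Adding the deaths equally gives (44.8 + 51.5) / (53.3 + 51.5) = 0.92. Adding them as recorded gives (44.8 + 54) / (53.3 + 49) = 0.97.
- At a VTE HR of 1.8 the split is 63.1 and 35.0. The ratio becomes (63.1 + 51.5) / (35.0 + 51.5) = 1.32 with equal deaths, or (63.1 + 54) / (35.0 + 49) = 1.39 with the recorded split.

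In both scenarios the ratio moves toward 1.

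**The case for a change.** The best case for a change is that this is a replication study and the fix is cheap. The label promises VTE death. Section 6.3.1 says that definitions are in Appendix A, and the visible appendix does not define that death. The comparative-analysis fields in Section 13 are empty, so no analysis of the point is visible. A relabelled outcome and a couple of defining sentences would cost almost nothing.

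Much of this stands. The nesting is real, the document does not settle the diagnosis position or the open-stay question, and the outcome is narrower than the trial's.

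The need for a change does not follow. The proxy is written out immediately under the label, so a reader of Section 6.3.1 can see that only deaths in VTE hospitalizations count. Section 1 says that replication is limited by what the databases hold, and Section 11 invites concerns about poorly measured variables. Because the components are also secondary outcomes, the plan already provides for separate results on them. The empty fields in Section 13 are for report names and dates, and Sections 11 and 12 are likewise unfilled, so they are weak evidence of an omission.

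The substantive additions bring no gain. The any-death analysis mixes in deaths that are not VTE and cannot estimate how many VTE deaths were missed. Reading the death component as VTE in any diagnosis position would be worse: 3,563 of 3,570 warfarin patients (99.8%) and 3,566 of 3,570 apixaban patients (99.9%) in the matched table already carry a PE code at baseline, so a code carried forward could turn an unrelated death into an event.

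**Conclusion.** No change is needed. The observation is right: on the natural reading the death component contributes essentially no first events, and the primary outcome is VTE hospitalization, fatal or non-fatal. But this is a matter of naming and missing detail. The plan discloses the proxy, and analysts who use the visible principal-position lists will arrive at the same event set whether or not the word mortality is in the label. Expected events stay at 98.1 and power at 0.965, and power is still 0.947 if one event in ten turned out to be death-only. No difference between arms is shown.

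This rests on two assumptions: that the external folder holds no different diagnosis-position rule for the death component, and that deaths in stays already open at the start of follow-up are few. Neither can be checked from the document. The number of VTE deaths outside a VTE stay cannot be derived either. When the result is set beside the trial, it should be read as a hospital-based outcome.
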